1. The list of patients admitted to Johns Hopkins Hospital (JHH), Johns Hopkins Bayview Medical Center (JHBMC), Howard County General Hospital (HCGH), and Suburban Hospital will be reviewed daily. We will query an electronic medical record (EHR) system to alert study investigators about patients admitted with any of the qualifying diagnoses to help with screening process. We will also query the list of the cardiac surgery operating room and cardiac catheterization lab to identify qualifying patients undergoing cardiac surgery or PCI procedure on an ambulatory basis. Furthermore, IRB approved flyers will be placed in clinician work rooms allowing clinicians to refer patients to the study. Patients who meet the inclusion criteria (see below in section 5) will be entered in the REDCap (Research Electronic Data Capture) database.
2. Study team members will subsequently screen patient charts for exclusion criteria. Before approaching eligible patients for consent, study team members will ask the attending physician of the patient to obtain permission from patients for the study team to approach them.
3. Patients will be approached in the hospital anytime during their index hospital admission or presentation for procedure.
4. Once patients are approached, further questions will be asked to screen for exclusion criteria including visual, motor, and/or auditory impairment limiting digital health technology use.
5. Written consent will be obtained at the bedside in the clinical units at participating sites. For patients who are not consent at bedside (e.g. patients undergoing same-day PCI procedure who have received sedation within preceding 24 hours), study team will follow up with a telephone call within 1 week after discharge to gauge interest in

participation. For interested patients, informed consent will be obtained remotely via Docusign.

6. Patients will be given detailed information and consent form to review during bedside or remote enrollment.
7. Sufficient time will be provided to the patient to read and understand the consent form with a repeat of information if necessary.
8. Patients will be given the opportunity to ask any questions to the research team while considering to participate in the study.
9. Patients with hearing, motor, and visual impairment will not be included (precludes meaningful use of intervention technology).

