10. The study team member will share with the patient that they can take as much time as necessary to understand the consent form. Study team members will then ask questions to the patient to clarify whether they understand the information provided in the consent form.
11. Once informed consent is obtained, an Epic documentation (Research note) and research flag will be placed in the EHR.
12. If the patient is non-English speaking, study participation will not be available, given the need for extensive communication needed during CR, especially hybrid CR.
13. After consent is obtained by the research team member and prior to randomization, baseline data (e.g. demographic information, relevant medical history, blood pressure, heart rate)) will be obtained.
14. Following hospital discharge, consented patients will be followed up with a telephone call during a 4-week run-in period to assess their continued interest in study participation, as well as to verify their insurance approval for in-center CR. Those who qualify will then be randomized at a 1:1 ratio to the intervention plus usual care (intervention group) or usual care alone (control group). Usual care is defined as care according to patient care team's standard practice. Randomization will be based on a dynamic randomization strategy that minimizes the difference in age, sex, and treatment modality (cardiac surgery, cardiac catheter-based procedure, or medical therapy alone).
15. If the order for CR referral is not done automatically, we will encourage the primary team to place the order for CR in the EHR and/or place the CR order on behalf of the primary team following attending physician approval, to ensure 100% CR referral rate for all study participants.
16. We will use a random number generator for generation of random number sequences and adopt open source software for dynamic randomization implementation. We will minimize bias by concealed allocation at time of enrollment.
17. Once randomization arm is determined, a study team member will inform each patient of their allocation.

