19. Individuals randomized to the intervention will receive personalized technology onboarding from a study team member. Depending on their level of technological literacy, patients will receive tailored video- and in-person guidance on how to download the app onto the phone, use the smartwatch [Apple Watch (FDA cleared) or Fitbit (FDA cleared)] and blood pressure monitor [Omron Blood pressure cuff (FDA cleared)] which will be paired with the smartphone via Bluetooth. The research team will have access to data on onboarding details as well as data collected via these devices, which will be reviewed during business hours on a daily basis. The participants will also be given a StartKit document which will include information on how to use the app to reference following discharge (Uploaded as supplementary document). Furthermore, patients will be provided with an email address and phone number to allow them to contact study investigators in case they have questions about technology use. They will also be able to submit feedback or questions regarding app use directly via the app. The patients will be encouraged to start using the app immediately but will be told to avoid unmonitored exercise until they have attended an in-person CR center for at least two visits, where risk stratification is performed based on AACVPR criteria (uploaded in Section 20.2). These two in-person sessions will serve as a basis for personalization of the home exercise plan, improving self-efficacy and confidence for home exercise, and assessment of safety for home exercise. If patients have any high risk features precluding home exercise, they will not be allowed to do home exercise as part of study intervention but they will be able to receive coaching calls, education and track medication intake via the app as well as work on modification of other cardiovascular risk factors. Additionally, they will be encouraged to continue attending in-person CR sessions for safe, monitored exercise, and will be advised to perform lower levels of usual physical activity (e.g., walking, range of motion exercises) as advised by the CR staff.
20. The initial phase of study participation in the hospital will be limited to study description and informed consent. All interventions will start following the 4-week run-in period, for those randomized to the intervention group.

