28. At 12 weeks post-randomization follow up, all study participants will receive a survey via REDCap to report any adverse events, including a heart attack, repeat cardiac procedure, stroke, transient ischemic attack, emergency room visit, or hospital readmission. If a patient is readmitted to a Hopkins affiliated hospital or other site's hospital, their EHR will be searched for confirmation and cause of readmission. If the person is readmitted to an outside hospital, we will email them an Authorization for Release of Health Information form asking for permission to obtain their EHR of readmission. If patients cannot be reached, we will contact their emergency contact to

identify whether the patient is alive and also search the EHR. If death is reported, it will be verified by death certificates or through the EHR.

29. At 12 weeks post-randomization follow up, all participants will attend an in-person study visit at Johns Hopkins Bayview Institute for Clinical and Translational Research (ICTR; Clinical Research Unit) site where all measurements outlined in Table 3 will be conducted, including vital signs, blood work for HbA1c and Lipid panel (non-fasting), body measurements, and 6MWT. If a participant cannot attend the final visit at Johns Hopkins Bayview ICTR site due to medical conditions, exceptions can be made to accommodate the participant at another study site. The 6MWT will be performed by ICTR staff blinded to study arm assignment to avoid bias in measurement (compared to the pre-discharge 6MWT for hospital-enrolled patients, which will be obtained by a trained study team member). Participants will be given an option to complete online surveys while attending the in-person study visit. If at either of these time points (baseline and 12 weeks post-randomization), participants do not respond to the online surveys within 7 days, a member of the study team will attempt to obtain their responses to the surveys via a phone interview. In order to accommodate flexible scheduling, we will aim to allow up to 24 weeks for the final study visit. For the ICTR study visit, parking and transportation fees will be covered by the research study budget for all patients.

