30. If the study engages additional sites in the future, local participant recruitment will be conducted by local research team members. Site specific research team members will undergo training prior to site activation and thus recruitment and onboarding to the DHI will be conducted in consistent manner. Decisions regarding patient management will be made by the patient care team.

31. For study participants in both the intervention and control groups, sociodemographic data as well as clinical data will be extracted from EHR (REDCap variable list is uploaded in section for supplementary documents).

Table 3. Study Visits and Measurements

Visit 1. Baseline visit (Data obtained by chart review, at the bedside and online surveys delivered via email through REDCap)	Visit 2. Virtual visit at 4 weeks (for Intervention Arm only)	Visit 3. 12-weeks post-randomization follow up visit (Data obtained at in-person visit and online surveys delivered via email through REDCap)
In-person Measurements		In-person Measurements
Weight		Weight
Height		Height
Blood pressure		Blood pressure
Heart rate		Heart rate
Waist & Hip circumference		Waist & Hip circumference
		6 min walk test
Electronic Medical Record Review		Laboratory values and chart review
Lipid panel within 30 days of enrollment*	Lipid panel	Lipid panel*

Date: 10.09.2024

Principal Investigator: [name], MHS

Application Number: IRB00308410

HbA1c within 3 months of enrollment*		HbA1c*
Baseline clinical characteristics**		Interval clinical events**
Surveys delivered via email through REDCap #		Surveys delivered via email through REDCap #
e-Health Literacy scale		e-Health Literacy scale
The Rapid Assessment of Physical Activity		The Rapid Assessment of Physical Activity
Rate Your Plate		Rate Your Plate
Patient-Reported Outcomes Measurement Information System (PROMIS) Global Health Scale v1.2		Patient-Reported Outcomes Measurement Information System (PROMIS) Global Health Scale v1.2
Patient Activation Measure 10 ³⁰		Patient Activation Measure 10 ³⁰
Patient Health Questionnaire (PHQ-8) ##		Patient Health Questionnaire (PHQ-8)
Generalized Anxiety Disorder 7 (GAD 7)		Generalized Anxiety Disorder (GAD 7)
Perceived Stress Score		Perceived Stress Score
Sociodemographic survey (education level, income level)		Sociodemographic survey (education level, income level)
Smoking status, quitting attempts		Smoking status, quitting attempts
		Electronic Medical Records and Corrie Health Platform User Analytics

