For the trial to demonstrate noninferiority with 80% power, assuming a pooled standard deviation of 107 meters for the follow-up 6MWT and a true 6MWT difference in favor of the Corrie HCR program of 30 m, 160 patients will be required (80 per group) to exclude a difference of >12.5 m in favor of the usual care group. The noninferiority margin of 12.5 m was chosen to represent about 40% of the minimum important difference of 30 m in 6MWT as identified in previous studies. Accounting for an attrition rate of 20% during follow-up after randomization, a total of 200 (100 per group) participants will be randomized in a 1:1 ratio to the 2 treatment arms. In order to accrue 200 patients for randomization, we expect to recruit up to 300 patients, until target randomization number has been met. We will compare the mean level of 6MWT at 12 weeks post-randomization between the intervention and control groups using a generalized linear regression model. The sample size calculation was performed using the TWOSAMPLEMEANS statement in SAS version 9.4 procedure PROC POWER (SAS Institute Inc., Cary, NC), in which the null value option was specified to represent the noninferiority margin.

If a participant has an adverse event that results in them being discontinued from the study or does not engage with the intervention, that participant will be included in the intention-to-treat analysis, which is the primary form of analysis for our study.

In addition to the primary intention-to-treat analysis, a pre-specified, per-protocol analysis will be conducted 1) inclusive of intervention group participants who remain active in the study and engage with the intervention, and separately 2) among those participants (in both control and intervention arms) who have completed at least two in-person CR sessions, in order to assess the efficacy of the intervention.

In addition, pre-specified subgroup analyses will be performed, stratified by: age, sex, treatment modality (cardiac surgery, catheter-based intervention, or medical therapy), and LDL-C level (threshold LDL-C \geq 55mg/dL).

8. Risks

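### A pre-discharge 6MWT is promised in item 29 but missing from Table 3, at odds with item 20, and given no role in the primary model; precision is forgone if the walk is done

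*Combined protocol and SAP*

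**What the plan says.** All references are to the combined protocol and SAP.

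- **Section 4, item 29** describes the 12-week 6MWT, done by blinded research-unit staff, and contrasts it with an earlier walk: "compared to the pre-discharge 6MWT for hospital-enrolled patients, which will be obtained by a trained study team member".
- **Table 3** has one 6MWT row, "6 min walk test", with an entry at Visit 3 only. Weight, height, blood pressure, heart rate and waist and hip circumference are entered at both Visit 1 and Visit 3.
- **Section 4, item 20**: "The initial phase of study participation in the hospital will be limited to study description and informed consent".
- **Section 4, item 13** gives examples of the data collected before randomization, "baseline data (e.g. demographic information, relevant medical history, blood pressure, heart rate", and the walk is not among them. The list is illustrative, so this is weak evidence either way.
- **Section 4, item 5** provides remote consent for patients not consented at the bedside: "study team will follow up with a telephone call within 1 week after discharge". Such patients cannot have a pre-discharge study walk.
- **Section 4, item 14** randomizes after a 4-week run-in, using minimization on age, sex and treatment modality.
- **Section 7**, on the primary analysis: "We will compare the mean level of 6MWT at 12 weeks post-randomization between the intervention and control groups using a generalized linear regression model". No covariate is named. The sample size is derived "assuming a pooled standard deviation of 107 meters for the follow-up 6MWT"; the assumed benefit of the intervention is 30 m, and the noninferiority margin is 12.5 m.

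**The concern.** The passages disagree on whether a participant enrolled in hospital walks before discharge. Staff working from Table 3 would not do the test; staff working from item 29 would. If practice differs between sites, the value will be missing by site.

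If the walk is done, it is a measurement of the primary endpoint's own variable, taken before randomization. Adjusting for it is legitimate and usually improves precision. Section 7 gives it no role, and the sample size takes no credit for it. Minimization limits imbalance that runs through age, sex and treatment modality. It does not control differences in walking capacity within those groups.

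At stake is the width of the confidence interval for a noninferiority comparison, and a check of baseline balance on the endpoint. Covariates should also be fixed in advance, so that the choice cannot be influenced by results.

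**Working it through.** **Inputs from Section 7:** SD of follow-up 6MWT 107 m; assumed benefit 30 m; margin 12.5 m; 80 evaluable per arm; attrition 20%. The significance level is not stated.

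**1. The plan's own figure.** The distance from the assumed effect to the margin is 30 + 12.5 = 42.5 m. By the normal formula at one-sided 5%, n per arm = 2 × [107 × (1.645 + 0.842) / 42.5]² ≈ 78.4, so 79. The noncentral-t calculation gives 80 per arm, or 160. Then 160 / 0.80 = 200. Both stated totals reproduce. At one-sided 2.5% the answers are 100 (normal) or 101 (t) per arm, which do not. One-sided 5% is therefore inferred, and the design is that of an unadjusted comparison.

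**2. Unadjusted precision.** SE = 107 × √(2/80) = 16.92 m. Power = Φ(42.5/16.92 − 1.645) = Φ(0.867) = 80.7% (80.4% by noncentral t). The 95% half-width is 1.96 × 16.92 = 33.2 m.

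**3. With adjustment.** Let f be the share of analysed patients with a pre-discharge walk and r its correlation with the 12-week walk. The documents give neither. Assume f = 60-80%, since the remote-consent route makes full coverage unlikely, and r = 0.3-0.6. With a missing-baseline indicator, the variance is multiplied by approximately 1 − f r².

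| f | r | 1 − f r² | SE (m) | Power, one-sided 5% |
|---|---|---|---|---|
| none | – | 1 | 16.9 | 80.7% |
| 0.6 | 0.3 | 0.946 | 16.5 | 82.6% |
| 0.8 | 0.3 | 0.928 | 16.3 | 83.2% |
| 0.6 | 0.6 | 0.784 | 15.0 | 88.3% |
| 0.8 | 0.6 | 0.712 | 14.3 | 90.9% |

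The 95% half-width falls from 33.2 m to 32.3-28.0 m. If the level were one-sided 2.5%, unadjusted power would be 71.0%, and the same range of f and r would give about 73-85%.

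**4. Chance imbalance.** If everyone had the walk, a one-standard-error difference between arms in baseline distance would move the unadjusted estimate by r × 107 × √(2/80) = r × 16.9 m. The baseline SD cancels. For r = 0.3-0.6 this is 5.1-10.2 m, before whatever part minimization removes. It is random error already contained in the SE of step 2, so it is not an additional loss.

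**The case against.** The strongest reply is that the walk may not exist. Its only mention is a parenthesis; the Visit 1 cell of Table 3 is blank and item 20 appears to exclude it. If the parenthesis is stray text, deleting it is the whole remedy and the calculation falls away. This stands, and it is why the recommendation is conditional. Item 20 cannot be read quite literally, however, because Table 3 itself places bedside measurements at Visit 1.

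Second, a reader might infer that the primary analysis is biased or the sample size wrong. The documents do not support that. Comparing 12-week means between randomized groups is unbiased without a baseline value, and 160/200 reproduces without one.

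Third, a reader might infer that the plan rejects adjustment. Section 7 is only silent: a regression model can carry covariates, and none is specified.

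Fourth, a reader might take this walk to be the best available predictor of the outcome, or take 107 m as the spread before treatment. Neither is in the documents. The 107 m is the SD of the follow-up distance, and no correlation is reported. The walk would come soon after infarction, surgery or a procedure and before the run-in, so the correlation could be modest.

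Fifth, power of about 93% follows from f = 100% and r = 0.6 (variance factor 0.64, SE 13.5 m), but the remote-consent route makes full coverage unlikely.

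Finally, minimization already covers the surgery, catheter-based and medical-therapy mix. That is correct; only residual imbalance within those groups remains.

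**Conclusion.** The point holds as a conflict between passages, joined to a conditional gain in precision. Items 20 and 29 and Table 3 do not agree on whether a pre-discharge 6MWT is taken, and Section 7 does not specify it as a covariate. Nothing here invalidates the primary comparison or the stated sample size.

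If the walk is done, adjustment would cut variance by about 5-29% and bring power to about 83-91%, from about 81%. This rests on assumed coverage of 60-80%, an assumed correlation of 0.3-0.6, the plan's own SD and effect, and an inferred one-sided 5% level. At the low end the gain is about two percentage points of power. It is worth taking because it costs almost nothing.

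**What to change.** First settle whether the pre-discharge 6MWT is done, and make items 20 and 29 and Table 3 agree.

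- **If it is done:** show it at Visit 1 in Table 3 for hospital-enrolled patients and amend item 20 to allow it. State in Section 7 that the primary 12-week 6MWT model adjusts for the pre-discharge distance, with a missing-baseline indicator for participants without one, alongside age, sex and treatment modality. Do not make change from that walk the endpoint: it is taken in acute recovery, by a different assessor, and is unavailable for remotely enrolled participants.
- **If it is not done:** delete the parenthesis in item 29.

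The first route costs one table entry, a small edit to item 20 and one or two sentences in Section 7, with no procedure beyond what item 29 already promises. The second costs one deletion. Either should be settled before outcomes are seen by arm.

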The Corrie DHI program consists of a patient-facing smartphone app which provides education; recommendations for lifestyle modifications; medication, vitals, and exercise monitoring; appointment scheduling and tracking; care team directory; electronic wallet for health and stent cards; the ability to send PDF summary reports to clinicians; and follow-up reminders to optimize cardiac recovery and secondary prevention. The original version of the Corrie Health digital platform was tested in acute MI patients at 4 clinical sites including Johns Hopkins Hospital, Johns Hopkins Bayview, Reading Hospital and Massachusetts General Hospital (MiCORE IRB00099938).¹³ Patient-monitored data flows into secure servers on the backend, providing a source of rich, granular data over time for heart rate, steps, weight, blood pressure, and medication adherence. Corrie is built on Apple and Android platforms.

For the present trial, the original Corrie Health digital platform was adapted to include extensive exercise tracking with pre-and post- exercise data capture along with weekly

Date: 10.09.2024

Principal Investigator: [name], MHS

Application Number: IRB00308410

evaluations and goal setting by a trained “Corrie Coach” to promote behavior change and mental health support. Exercise can be performed anywhere a patient feels comfortable with, including neighborhood gyms or outdoors. Furthermore, patients will be provided with motivational messaging and feedback on progress with their goals. The Corrie Message Bank (attached as supplemental document) has been developed by combining validated messages from the mActive trial,³³⁻³⁵ American Heart Association’s Care Pathway messages, and patient generated messages. The Corrie Clinical Dashboard allows for intuitive data visualization by the clinician of key cardiovascular health metrics including blood pressure, heart rate, steps, medication adherence, exercise, and education completion. The clinician then uses this data to generate actionable insights and provide comprehensive feedback to the patient. The trial intervention has been optimized with input from demographically diverse patients, caregivers and clinicians (IRB00266731). A preliminary version of the intervention is being evaluated in our IRB approved quality improvement project (IRB00248849). Preliminary data from the quality improvement project supports that it is feasible to evaluate the intervention in a RCT.

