27. All patients randomized to the intervention will receive weekly virtual check-ins consisting of a video call (unless patient opts out of the video component for only audio call) from a trained exercise physiologist health coach, starting within 1 week from randomization. These virtual check-ins will be used to guide patients with individualized risk factor modification, stress reduction and on adapting their exercise prescription (for those cleared for home exercise), where the latter will be performed by a study exercise physiologist. If during the virtual check-in the patient reports high risk symptoms (e.g. chest pain), the health coach will follow Cardiac Rehabilitation Standard Operating Procedure scenarios (attached in supplementary documents) to handle the different emergencies, and they will be asked to pause the exercise component of the intervention until safety of returning to exercise is determined by their caring clinician. The Corrie Dashboard will be monitored once a day and any red flags will be handled similarly as per the Standard Operating Procedure. Patients will be informed that the study team cannot replace their care teams and patients should contact their clinicians, call 911 or go to emergency room when experiencing severe symptoms or abnormal vital signs. Virtual, synchronous, audiovisual group-based education sessions will be offered weekly by the exercise physiologist health coach. These sessions will supplement the weekly virtual check-ins for patients randomized to the intervention. These educational, patient-support/social networking forums aim to enhance the social experience of this virtual model. Social media platforms (such as Facebook group), moderated by the study team, may be used to facilitate voluntary communication and interaction among study participants for community-building purposes.

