Each participant will be enrolled in the study from the time of enrollment during or shortly following hospitalization or cath lab encounter to 12 weeks post-randomization after discharge. Study visits will occur at baseline (at patient bedside or via follow up call) and 12 weeks post-randomization post-discharge (at Bayview Clinical Research Unit, up to maximum 18 weeks post- (to account for delays related to clearance of procedure-related precautions (e.g. sternal precautions following CABG surgery) or insurance approval for starting in-person CR sessions), whichever occurs earlier). Patients in the intervention arm will also be encouraged to have a lipid panel rechecked (ordered by the primary team at discharge) at their local laboratory 4 weeks post-discharge. Patients in the control group will receive reminders from the study team to participate in the final study visit.

Date: 10.09.2024

Principal Investigator: [name], MHS

Application Number: IRB00308410

Blinding

Although blinding participants or study team members enrolling patients is not possible, outcome assessors will be blinded to intervention allocation. We will instruct study participants not to discuss allocation with study personnel prior to both the initial and follow-up assessments.

Definition of treatment failure or participant removal criteria

For participants in the intervention group: If the participant stops using the Corrie DHI for >30 days or does not respond to phone calls after failing to complete the study surveys after 7 days, the participant will be considered lost to follow up.

For participants in the Control group: If the participant does not respond to phone calls after failing to complete the study surveys after 7 days, the participant will be considered lost to follow up.

Description of what happens to participants receiving therapy when study ends or if a participant's participation in the study ends prematurely

When the study ends or a participant's participation in the study ends prematurely, participants in the intervention group may keep their app (in which case their use will continue to be tracked). Any other devices that were provided during the study will be expected to be returned.

Participants may be given the option to participate in future research studies.

5. Inclusion/Exclusion Criteria

Inclusion Criteria

- Adult aged 18 years or older

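### Reminders for the final 6MWT visit are stated for the control group and not for the intervention group, so retention effort for the primary endpoint is arm-specific as written and could bias the noninferiority comparison in either direction.

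*Combined protocol and SAP*

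**What the plan says.** The reminder sentence is in Section 4, under the heading on study duration and number of visits: "Patients in the control group will receive reminders from the study team to participate in the final study visit". The document has no matching sentence for the intervention arm.

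The visit itself is for everyone. Section 4, item 29: "At 12 weeks post-randomization follow up, all participants will attend an in-person study visit". Travel support is also equal: "parking and transportation fees will be covered by the research study budget for all patients".

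Other contacts could bring intervention participants back:

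- Item 27: "All patients randomized to the intervention will receive weekly virtual check-ins consisting of a video call", starting within a week of randomization.
- Section 3: the app provides "follow-up reminders to optimize cardiac recovery and secondary prevention".
- Item 29, both arms: if surveys are unanswered after 7 days, "a member of the study team will attempt to obtain their responses to the surveys via a phone interview".

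None of these is described as a reminder for the 6MWT visit.

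Two further statements bear on non-engagers. In Section 4, under treatment failure and participant removal, more than 30 days without use of the digital program is enough to class an intervention participant as lost to follow-up; controls have no comparable non-use trigger. Section 7, by contrast, says of a participant who stops because of an adverse event or who "does not engage with the intervention, that participant will be included in the intention-to-treat analysis".

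**The concern.** The primary endpoint is a walk distance measured in person at one visit. A phone survey cannot replace it, and Section 7 gives no method for a missing value. Retention at that visit is therefore the main protection for the intention-to-treat comparison, and the plan states the retention procedure for one arm of an open-label trial.

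The people for whom the gap matters most are intervention participants who have disengaged. Coaching and the app may serve as the channel for engaged participants. For those who no longer use the app, the text names no contact aimed at the visit, and the 30-day rule may lead staff to stop pursuing them. If the missing rates then differ between arms, and those missing walk less far than those retained, the observed difference shifts. With a margin of only 12.5 m, a shift of a few meters matters. A shift toward the intervention raises the chance of a false noninferiority claim; a shift the other way costs power.

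**Working it through.** **Inputs from Section 7:** SD 107 m; assumed true difference 30 m in favor of the intervention; margin 12.5 m; power 80%; 80 per group evaluable; 20% attrition, not split by arm; 100 per group randomized. Alpha is not stated.

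**1. Reproduce the plan's sample size.** n per arm = 2 × (z for 1 − alpha + z for 0.80)² × SD² / (30 + 12.5)².

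- One-sided 0.05: 2 × (1.645 + 0.842)² × 107² / 42.5² = 78.4, so 79. The noncentral-t version gives exactly 80 (power 0.804).
- One-sided 0.025: 99.5, so 100, or 101 by noncentral t. Power at 80 per arm would be 0.704, so this does not reproduce.
- Attrition: 160 / 0.80 = 200.

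The plan's 160 and 200 are reproduced at one-sided 0.05, which I use below as an inferred value.

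**2. Bias formula.** Let p be the missing proportion in an arm and D the amount by which the mean walk of those missing falls short of the mean of those retained. The full-arm mean is then the retained mean minus p × D, so the observed mean is too high by p × D. With D equal in both arms, the bias in intervention minus control is

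bias = (p intervention − p control) × D.

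Equal loss or D = 0 gives zero. Higher control loss reverses the sign, as does a negative D with higher intervention loss.

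**3. False-noninferiority rate.** At a true difference of −12.5 m the rate is 1 − Φ(1.645 − bias / SE), with SE = 107 × √(1/n intervention + 1/n control).

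**4. Illustration.** The documents give neither arm-specific attrition nor the walk distance of disengaged participants, so both are assumed. Each row below averages 20% missing. For 25% vs 15% in either direction, SE = 107 × √(1/75 + 1/85) = 16.95 m. For 30% vs 10%, SE = 107 × √(1/70 + 1/90) = 17.05 m.

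| Missing, intervention vs control | D | Bias | Share of 12.5 m | False-noninferiority rate |
|---|---|---|---|---|
| 20% vs 20% | any | 0 m | 0% | 5.0% |
| 25% vs 15% | 30 m | +3.0 m | 24% | 7.1% |
| 25% vs 15% | 60 m | +6.0 m | 48% | 9.8% |
| 30% vs 10% | 30 m | +6.0 m | 48% | 9.8% |
| 30% vs 10% | 60 m | +12.0 m | 96% | 17.3% |
| 15% vs 25% | 30 m | −3.0 m | 24% | 3.4% |
| 15% vs 25% | 60 m | −6.0 m | 48% | 2.3% |

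**5. Power.** From imbalance alone, with total loss fixed, power hardly moves: 80.7% at 20/20, 80.6% at 25/15, 80.2% at 30/10 (normal approximation). The issue is bias, and a larger sample would not remove it. In the reversed case the bias itself costs power: Φ((42.5 − 3) / 16.95 − 1.645) = 75%, and with 6 m it is 69%.

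**The case against.** The sentence does not say that reminders go to controls alone. Controls have no scheduled coaching, so it may simply fill a contact gap in the low-contact arm. The weekly calls are initiated by the study and offered to all intervention participants, and nothing says they cease when app use does. Several contacts around 12 weeks apply to both arms: the emailed surveys, the phone calls to survey non-responders, and the call to an emergency contact when a participant cannot be reached (item 28). Section 10 has the team ask for devices back after a week of non-engagement, which is itself a contact with disengaged participants. It also pays every participant a gift card after the final visit. Incentives are therefore equal, and the intervention arm's greater overall contact could make its retention better than that of controls.

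Most of this stands, and it limits what can be claimed. A reader might infer that disengaged intervention participants get no reminder at all. That is an inference from silence; the documents neither state nor exclude it. A reader might also infer that the resulting loss would favor the intervention. That needs both excess intervention loss and shorter walks among those lost, and the documents give neither. Nor can the bias be sized from intervention losses alone: with 20% attrition planned overall, only loss in excess of control loss counts.

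The objection does not remove the asymmetry in the text. Survey calls are made to collect survey answers, and no stated intervention-arm contact is directed at the walk. The 30-day classification applies to one arm only and sits badly with the intention-to-treat statement.

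**Conclusion.** The point holds as a gap in the written procedure. Reminders for the primary-endpoint visit are stated for one arm, the text is silent for the other, and a non-use rule in that other arm could end pursuit of participants whom the primary analysis is meant to include. This could bias the noninferiority comparison in either direction.

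Its size cannot be read from the documents. Under the assumed 25% vs 15% missing and a 30-60 m deficit, it is 3-6 m toward the intervention and a false-noninferiority rate of about 7%-10% instead of 5%. Those figures rest on a complete-case analysis, the same deficit in both arms, and the inferred one-sided alpha of 0.05. Zero and negative bias are equally compatible with the text. The change is worth making because it is nearly free and protects the one measurement on which the trial's claim depends.

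**What to change.** Replace the control-group sentence in Section 4 with one final-visit reminder schedule that is identical in both arms: same days, same route (for example automated from REDCap), regardless of app use, coaching contact or the 30-day non-use classification. State there that this classification does not end efforts to obtain the 12-week walk, so that it agrees with the intention-to-treat statement in Section 7. Report final-visit completion by arm and, within the intervention arm, by engagement.

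The planned 160 evaluable and 200 randomized do not change. The cost is a rewritten passage and automated reminders for about 100 more participants. If intervention participants are already reminded, the edit only records practice. Equal reminders lower the risk of differential loss but do not guarantee equal loss, so a stated method for a missing 6MWT is still needed.
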